- Any single instance of AST or ALT $> 3 \times$ ULN AND total bilirubin $> 2 \times$ ULN that is NOT thought to be due to disease progression or other medical illness
- For subjects with documented hepatic metastases and a baseline AST or ALT $> 3x$ upper limit of normal (ULN) any single instance of AST or ALT $> 5 \times$ ULN AND total bilirubin $> 2 \times$ ULN that is NOT thought to be due to disease progression or other medical illness

The guidelines for assessment of Drug-Induced Liver Injury are described in [Appendix F](#).

Cardiac DLT Criteria

The following cardiac AEs that are not clearly and incontrovertibly due to disease progression or extraneous causes (e.g., accidental injury or similar event) are considered DLTs:

- LVEF below institutional limits and $\geq 10\%$ points below pre-treatment baseline

- Grade 2 symptomatic heart failure

The first DLT will result in withholding of the drug until recovery of the ejection fraction to prior levels. If subjects remain off ZW25 for more than 4 weeks they will be removed from the study. For the management of left ventricular dysfunction, see [Section 5.2.3.1](#).

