5.2.3 Dose Modifications of ZW25

An individual subject who experiences an event that meets the criteria for DLT (defined in [Section 3.1.2](#)) at any time on study treatment may continue at a step-down dose (or an intermediate dose level determined by the SMC) once the toxicity has returned to Grade 1 or baseline with approval of the medical monitor. If the subject then experiences another such event at the step-

down dose level, with approval from the medical monitor, the dose of ZW25 administered to that individual subject should be reduced again but should not go below 10 mg/kg Q2W.

For Part 2 of the study, dose modifications for ZW25-associated toxicity are presented in [Table 5](#) below. Dose decreases or delays for other reasons may be permitted with approval from the medical monitor. The reason for dose decrease or delay must be recorded, and the sponsor must be notified. Up to 2 dose reductions per subject will be allowed for Q2W dosing, but the reduced dose cannot be lower than 10 mg/kg Q2W.

There must be a minimum of 10 days (± 2 days) between doses. Day 15 doses not administered within 6 days after Day 15 must be skipped.

Note: Although only 1 step-down dose level (not lower than 15 mg/kg Q2W) of ZW25 is allowed in the study at a cohort level, individual subjects may have up to 2 dose reductions as long as the reduced dose is not lower than 10 mg/kg Q2W.

Table 5: Recommended Management and Potential Dose Modifications for ZW25-Associated Toxicity

Adverse Event Related to ZW25	Action for ZW25
Grade 1 or Grade 2 nausea and vomiting	
 • Suggest a 5-hydroxytryptamine (5-HT₃) receptor antagonist until resolution of symptoms, or a prochlorperazine. • No dose modification of ZW25 is required. • For breakthrough nausea or vomiting, consider olanzapine 5 or 10 mg daily for three days. For subjects already receiving olanzapine, prochlorperazine may be used.

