5.2.3.1 Left Ventricular Dysfunction

Management of left ventricular dysfunction, regardless of relationship to study drug, is described in [Table 6](#).

Table 6: Management of Left Ventricular Dysfunction

Left Ventricular Dysfunction (Regardless of Causality)	Action for ZW25
Symptomatic cardiac heart failure	
 • Discontinue ZW25
LVEF <40%	
 • Do not administer ZW25 • Repeat LVEF assessment within 4 weeks • If LVEF <40% is confirmed, discontinue ZW25
LVEF below institutional limits of normal and absolute decrease of \geq 10% points below pre-treatment baseline	
 • Do not administer ZW25 • Repeat LVEF assessment within 4 weeks • If the LVEF has not recovered to within 10% points from baseline, discontinue ZW25
LVEF 40% to \leq 45% and absolute decrease is < 10% points from baseline	
 • Continue treatment with ZW25 • Repeat LVEF assessment within 4 weeks
LVEF > 45%	
 • Continue treatment with ZW25, as applicable

LVEF = left ventricular ejection fraction

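### For symptomatic heart failure, Sections 3.1.2 and 5.2.3 leave a way back to ZW25, while Table 6 requires that it be stopped, and no order of precedence is stated

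*Combined protocol and SAP*

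**What the plan says.** Three places in the protocol say what happens to ZW25 after symptomatic heart failure.

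- **Section 3.1.2, Cardiac DLT Criteria.** Two events are listed: an LVEF fall, and "Grade 2 symptomatic heart failure". The text that follows does not separate them: "The first DLT will result in withholding of the drug until recovery of the ejection fraction to prior levels". It continues: "If subjects remain off ZW25 for more than 4 weeks they will be removed from the study". It ends with a pointer: "For the management of left ventricular dysfunction, see" Section 5.2.3.1.
- **Section 5.2.3, first paragraph.** A subject with an event meeting the DLT criteria "at any time on study treatment may continue at a step-down dose (or an intermediate dose level determined by the SMC"). Two conditions attach: the event must first have settled to Grade 1 or to its pretreatment level, and the medical monitor must agree. No type of event is excepted.
- **Section 5.2.3.1, Table 6.** The lead-in reads: "Management of left ventricular dysfunction, regardless of relationship to study drug, is described in" Table 6. For the row "Symptomatic cardiac heart failure" the only action is to discontinue ZW25. That row has no hold, repeat test or rechallenge. A separate row covers the LVEF fall: hold, repeat within 4 weeks, and discontinue if LVEF has not come back to within 10 percentage points of baseline.

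**The concern.** An investigator with a subject in heart failure finds a hold with a recovery test in one section, a conditional step-down in another and a permanent stop in a third. Two of the three leave a way back to ZW25.

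The recovery test in 3.1.2 also does not fit the event. Heart failure is listed separately from the LVEF fall, so it can occur without the LVEF criterion being met. A test based only on ejection fraction could then be passed while symptoms persist. This sits badly with the caution elsewhere in the protocol: exclusion criterion 10 bars anyone with a history of symptomatic congestive heart failure, and Section 1.8.1 notes LVEF decreases with other HER2 inhibitors.

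The main stake is subject safety. The second is consistency of reporting. The same event, an AESI under Section 7.7.2, could be recorded as a ZW25 reduction, a ZW25 discontinuation or neither, depending on which text was followed.

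**Working it through.** The protocol gives no figure to reproduce here, so the check compares the texts and then traces what each route does to the summaries.

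**Step 1. The instructions for Grade 2 symptomatic heart failure, side by side**

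| Source | ZW25 action | Return to ZW25? |
|---|---|---|
| 3.1.2 | Hold until ejection fraction is back to its prior level; removal after more than 4 weeks off | Left open within 4 weeks; no dose named |
| 5.2.3 | Step-down after recovery to Grade 1 or baseline, with medical monitor approval | Permitted |
| Table 6 | Discontinue, regardless of causality | No |

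The 4-week sentence names ZW25. That identifies the drug being withheld and implies that a shorter interruption can end in resumption.

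**Step 2. Dose implied by each route, from a 20 mg/kg start**

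- 5.2.3, first event: 15 mg/kg or an intermediate level. 15/20 = 75%, so 75% to under 100% of the starting dose.
- 5.2.3, second event: not below 10 mg/kg. 10/20 = 50%.
- Table 6: 0.
- 3.1.2: no resumption dose given, so an unchanged dose is not ruled out.

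**Step 3. Effect of one event on the Section 9.3.9.1 ZW25 counts**

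| Route followed | Reductions | Discontinuations |
|---|---|---|
| Table 6 | 0 | +1 |
| 5.2.3 step-down | +1 | 0 |
| 3.1.2, resumed at unchanged dose | 0 | 0 |

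A count of one in n subjects is 1/n:

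- Part 1 cohort of 6 treated: 1/6 = 16.7 points.
- Part 1 cohort of 8 treated (assuming two replacements): 1/8 = 12.5 points.
- Part 2 safety analysis, 50 subjects plus 6 from Part 1 at the recommended dose: 1/56 = 1.8 points. This assumes that the first paragraph of 5.2.3 applies in both parts, since the heading of 3.1.2 limits that section to Part 1.

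Both proportions move only when Table 6 is compared with the 5.2.3 step-down. Against resumption at an unchanged dose, only the discontinuation proportion moves.

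**Step 4. What does not move**

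The event is one DLT whether ZW25 is held, reduced or stopped. The change in the DLT count against the 2-of-6 rule is therefore 0. The AESI count, the sample size and the definition of PFS6 do not depend on the action taken.

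**Step 5. A related mismatch for the other cardiac DLT**

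For the LVEF fall, 3.1.2 asks for return to the prior level, whereas Table 6 accepts return to within 10 percentage points of baseline. The 3.1.2 sentence is out of line with Table 6 for both cardiac events.

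**The case against.** The best defence is that the intended order can be recovered. The release test in 3.1.2 concerns ejection fraction, which fits the LVEF fall and not symptoms. The same paragraph sends the reader to 5.2.3.1, where Table 6 has its own row for heart failure. Section 5.2.3.1 sits inside 5.2.3, so the general step-down paragraph can be read as yielding to the specific rules beneath it. The step-down is also discretionary and needs medical monitor approval.

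Much of this stands. It makes Table 6 the likelier intention and makes free divergence between sites less likely. It does not settle the matter. The hold sentence is itself specific to cardiac DLTs, so a rule that specific text beats general text does not clearly favour Table 6. The pointer follows an instruction already given. The monitor's approval is no safeguard if the monitor relies on the same unqualified paragraph.

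A reader might infer three stronger things that the documents do not support:

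- **That a site following 3.1.2 will restart ZW25.** The section directs a hold, sets a 4-week limit and neither orders a restart nor names a dose. Resumption is left open, not required.
- **That ZW25 reduction and ZW25 discontinuation are both Part 1 primary endpoints.** Section 2.1 names ZW25 dose reductions, and separately treatment discontinuations due to AEs. Section 4.4.1 lets subjects stop one component and continue the others, and nothing says whether stopping ZW25 alone counts as a treatment discontinuation. ZW25-specific discontinuation appears in the 9.3.9.1 summary.
- **That pneumonitis/ILD and Grade 4 infusion reactions are in equal conflict.** For these, 5.2.3 offers only a discretionary permission beside specific stop rules (Sections 5.3.3 and 5.5; Table 7), and both can be obeyed by not using the permission. Section 3.1.2 also directs infusion reactions to 5.2.3.2. These overlaps are secondary.

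**Conclusion.** The inconsistency is real and is confined to symptomatic heart failure. Section 3.1.2 and Section 5.2.3 leave open re-dosing that Table 6 rules out, and the protocol does not say which prevails. Table 6 is probably meant to govern.

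This is first a matter of subject safety, and it should be corrected. Its statistical reach is small: one event can change category in the ZW25 exposure summary, worth 16.7 points in a cohort of six treated subjects and 1.8 points among 56. Those figures are for a single hypothetical event. The documents give no rate of heart failure with this combination, so no expected number is claimed. Of the quantities affected, only ZW25 dose reductions are named outright as a Part 1 primary endpoint. It would be wrong to infer that the dose-finding decision is compromised, because DLT counting and the 2-of-6 rule are unaffected, as are sample size and PFS6.

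**What to change.** Two short edits.

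1. **Section 3.1.2, Cardiac DLT Criteria.** Limit the withholding sentence to the asymptomatic LVEF criterion. Replace its recovery test with that of Table 6, return to within 10 percentage points of baseline. Add that symptomatic heart failure leads to ZW25 discontinuation per Table 6.
2. **Section 5.2.3, first paragraph.** Add that the step-down permission does not apply to events for which Table 6, Table 7, Section 5.3.3 or Section 5.5 requires discontinuation. This also closes the secondary overlaps for pneumonitis/ILD and Grade 4 infusion reactions.

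The cost is a few lines of protocol text. No new data, visits or analyses are needed.

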The overall study design is presented in [Figure 2](#). Each treatment cycle of ZW25 combined with palbociclib plus fulvestrant is 28 days. If any component(s) of the combination therapy is discontinued due to toxicity deemed related to the component(s), subjects on either part of the study may continue to receive the other component(s) of the study regimen until disease progression or start of subsequent anticancer therapy. (Note: trastuzumab, alternate CDK4/6 inhibitors, or any other treatment not part of the study regimen will be considered subsequent anticancer therapy. Palliative radiotherapy to a non-target bone lesion that is not progressing is allowed after the second cycle of treatment and must be administered after the initial response assessment obtained per protocol. This will not be considered subsequent anticancer therapy but must not interfere with the assessment of tumor target lesions. Treatment with palbociclib should be interrupted during palliative radiotherapy). Subjects who discontinue treatment with all 3 drugs for any reason (except death or withdrawal of consent) on either part of the study will have an end-of-treatment (EOT) visit within 14 days after the last dose of study drug (ZW25, palbociclib, and/or fulvestrant) and safety follow-up visit at approximately 30 days after the last dose of study drug. Subjects who discontinue all study treatment on either part of the study for reasons other than progressive disease or start of subsequent anticancer therapy will continue in follow-up with disease assessments approximately every 8 weeks after the previous scan until disease progression or start of subsequent anticancer therapy. If subjects enter this follow-up period before 24-weeks have elapsed since the start of study treatment, a disease assessment must be done at 24-weeks from the start of treatment (not required if ≤ 4 weeks since last disease assessment or if disease progression has already been documented). Responses that are initially observed during this follow-up period should be confirmed with disease assessment 4 weeks (+1

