3.1.2 Dose-Limiting Toxicity Evaluation and Determination of Recommended Dose Level (Part 1 only)

The DLT-evaluation period will be the first 28 days of treatment.

The dose level (evaluated dose of ZW25 plus evaluated dose of palbociclib and fulvestrant) will be considered not tolerated if ≥ 2 of 6 DLT evaluable subjects experience a DLT. If DLTs are observed in ≥ 2 subjects, the SMC may recommend a step-down dose level of 15 mg/kg Q2W or other dose not lower than 15 mg/kg Q2W for evaluation in up to 6 additional DLT evaluable subjects. Additionally, the SMC may recommend evaluation of step-down doses of palbociclib of 100 mg PO QD and/or 75 mg PO QD with or without recommending evaluation of a step-down dose of ZW25. There is no step-down dose for fulvestrant at a cohort or study population level; however, individual subjects who develop moderate hepatic impairment (Child-Pugh Class B) while on study treatment will have their fulvestrant dose reduced to 250 mg. Intermediate dose levels of ZW25 and/or palbociclib may also be recommended by the SMC. The SMC may recommend step-down doses for 1 or more of the drugs in the combination regimen at any time based on the overall safety profile. The dose of ZW25 is allowed to be de-escalated by a maximum of 1 step-down dose as recommended by the SMC. The dose of

palbociclib is allowed to be de-escalated by a maximum of 2 step-down doses as recommended by the SMC. At a reduced dose level, if 1 or fewer of the 6 subjects experience a DLT, then the dose level may be confirmed as recommended for Part 2. When necessary, more than 6 subjects may be enrolled in a given dose level to better characterize the safety profile of a particular dose level. The study will advance to Part 2 based on SMC recommendation. The DLT evaluation schema is presented in Figure 3. Additional safety experiences in later cycles may be considered when confirming the recommended dose level (ZW25 in combination with palbociclib plus fulvestrant) for Part 2.

Figure 3: DLT Evaluation Schema (Part 1 Only)

DLT= dose-limiting toxicity; RD=recommended dose; SMC=Safety Monitoring Committee

*The roles, responsibilities and functioning of the SMC are described in more details in the SMC charter.

** Step-down dose levels of ZW25 and/ or palbociclib as recommended by the SMC.

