4.4.1 Discontinuation of Study Treatment

If any component(s) of the combination therapy is discontinued due to toxicity deemed related to the component(s), subjects on either part of the study may continue to receive the other component(s) of the study regimen until disease progression or start of subsequent anticancer therapy (Note: trastuzumab, alternate CDK4/6 inhibitors, or any other treatment not part of the study regimen will be considered subsequent anticancer therapy. Palliative radiotherapy to a non-target bone lesion that is not progressing is allowed after the second cycle of treatment and must be administered after the initial response assessment obtained per protocol. This will not be considered subsequent anticancer therapy but must not interfere with the assessment of tumor target lesions. Treatment with palbociclib should be interrupted during palliative radiotherapy). Subjects who discontinue treatment with all 3 drugs for any reason (except death or withdrawal of consent) on either part of the study will have an end-of-treatment (EOT) visit within 14 days after the last dose of study drug (ZW25, palbociclib, and/or fulvestrant) and safety follow-up visit at approximately 30 days after the last dose of study drug.

Study treatment may be discontinued for any of the following reasons:

- Adverse event (AE)
- Death
- Lost to follow-up
- Withdrawal of consent
- Physician decision (non-AE, non-progressive disease)
- Pregnancy
- Progressive disease (either radiographic or clinical progression)
- Protocol violation
- Study termination by sponsor
- Other, non-AE

Also, if a subject has not taken ZW25 for more than 4 weeks, he/she will be withdrawn from study treatment unless approval is obtained from the medical monitor to continue on study treatment.

Also, if a subject starts subsequent non-study anticancer therapy, then study treatment will be discontinued before the start of the new therapy

At a minimum, all efforts should be made for subjects to complete the EOT visit ([Section 6.4](#)) and the safety follow-up visit ([Section 6.5](#)), and efficacy ([Section 6.6](#)) and survival follow-ups ([Section 6.7](#)).

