4.4.2 Subject Withdrawal from Study

Any subject may be discontinued from the study for any of the following reasons:

- Death
- Lost to follow-up
- Withdrawal of consent
- Study termination by sponsor

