6.6 Efficacy Follow-up (Every 8 weeks)

Subjects who have discontinued all study treatment on either part of the study for reasons other than progression or start of subsequent anticancer therapy will continue in follow-up with disease assessments approximately every 8 weeks after the previous scan until disease progression or start of subsequent anticancer therapy. The efficacy follow-up will include the following assessments:

- Disease assessment per RECIST 1.1 (CT/MRI scans, and breast cancer serum tumor markers [if being monitored])
- Bone scan (scintigraphy): For subjects with new lesions identified by post-baseline bone scintigraphy, targeted assessment by X ray, CT scan with bone windows, or MRI will be performed to confirm findings.
- Brain scan (MRI): After screening, brain scans will be required per protocol only for subjects with findings on the screening brain scan; for subjects without findings on the screening brain scan, subsequent brain scans will be done per institutional standard of care.
- ADA sample (only if a subject had an ongoing anti-ZW25 ADA present at the safety follow-up visit): These will be discontinued after the resolution of ADA.

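### The Part 1 cardiac DLT text removes subjects from the study where the rest of the protocol withdraws them from treatment only, and the cardiac hold, resume and stop rules do not fully agree (minor internal inconsistency)

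*Combined protocol and SAP*

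**What the plan says.** Section 3.1.2 applies to Part 1 only and fixes the window: "The DLT-evaluation period will be the first 28 days of treatment". It lists two cardiac DLTs: an LVEF below institutional limits and at least 10 points under the pre-treatment value, and Grade 2 symptomatic heart failure. It then gives two instructions, "The first DLT will result in withholding of the drug until recovery of the ejection fraction to prior levels" and "If subjects remain off ZW25 for more than 4 weeks they will be removed from the study", and refers to Section 5.2.3.1 for managing left ventricular dysfunction.

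Other sections cover the same ground:

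- Section 4.4.1: "if a subject has not taken ZW25 for more than 4 weeks, he/she will be withdrawn from study treatment unless approval is obtained"; that approval is the medical monitor's to give. It also asks that every effort be made to complete the end-of-treatment, safety, efficacy and survival follow-up.
- Section 4.4.2: "Any subject may be discontinued from the study for any of the following reasons", followed by death, loss to follow-up, withdrawal of consent and termination by the sponsor.
- Section 6.6: subjects who stop all treatment without progression or new therapy "will continue in follow-up with disease assessments approximately every 8 weeks after the previous scan". If they enter that follow-up before week 24, Section 3.1 adds that "a disease assessment must be done at 24-weeks from the start of treatment", with stated exceptions.
- Section 7.7.2: AESIs, which include LVEF falls of at least 10 points and symptomatic heart failure, are followed until they resolve or return to baseline.
- Section 5.2.3: a subject with a DLT-type event at any time may continue at a step-down dose once the toxicity has settled, with medical monitor approval. Heart failure is not excepted.
- Table 6 (Section 5.2.3.1): discontinue ZW25 for symptomatic heart failure. For an LVEF below the institutional limit with a fall of at least 10 points, hold, repeat within 4 weeks, and discontinue unless it has come back to within 10 points of baseline. For an LVEF above 45%, continue, as applicable.

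**The concern.** Leaving treatment and leaving the study are separate events in this protocol, each with its own section. Section 3.1.2 attaches the second to a toxicity trigger that Section 4.4.1 attaches to the first. A site following Section 3.1.2 literally would stop following a subject because of a cardiac event, although Section 7.7.2 requires that event to be followed to its end. Scans and survival contact would stop as well.

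The instructions on ZW25 itself also differ. For symptomatic heart failure, one text points to a hold until recovery and another to permanent discontinuation. For LVEF falls, the recovery tests differ, and two Table 6 rows can give opposite actions for one measurement. What is at stake is consistent cardiac safety handling with a HER2-directed antibody, more than any efficacy estimate.

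**Working it through.** The plan gives no figure on this point to reproduce. The check sets the rules side by side and works out where they diverge.

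**1. More than 4 weeks off ZW25**

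| | Section 3.1.2 | Sections 4.4.1 and 4.4.2 |
|---|---|---|
| Subject leaves | the study | study treatment |
| Exception | none | medical monitor approval |
| Listed as a reason to leave the study | implied | no |

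Even if Section 3.1.2 means study treatment, the missing approval exception remains a difference.

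**2. Reach of the removal sentence.** The DLT window is Days 1–28. The first post-baseline echocardiogram/MUGA in Appendix A is Cycle 3 Day 1, which is 28 + 28 + 1 = Day 57 (±7 days) and so falls outside it. Within the window, the trigger is therefore symptomatic heart failure or an unscheduled LVEF measurement.

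The 4 weeks run out as follows, depending on how they are counted:

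- last dose Day 1: 1 + 28 = Day 29
- last dose Day 15, or first withheld dose Day 15: 15 + 28 = Day 43
- first withheld dose Day 29: 29 + 28 = Day 57

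The first scheduled scan is Cycle 2 Day 28 = Day 56 (window 49–63). Week 24 is 24 × 7 + 1 = Day 169. Scans tied to the end-of-treatment or safety visit would normally still be done; a week-24 scan after removal would not.

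**3. Withholding against Table 6**

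- LVEF-fall DLT: the trigger matches the Table 6 hold row, and both texts withhold. Only the recovery test differs. Section 3.1.2 asks for return to an undefined earlier level; if that means baseline B, recovery is LVEF ≥ B. Table 6 recovery is LVEF ≥ B − 10. In whole numbers they disagree from B − 10 to B − 1: 50–59% for an assumed B of 60%, and 45–54% for B of 55% (the lowest value in each range is the boundary of within 10 points).
- Symptomatic heart failure: Section 3.1.2, by its own list, withholds until recovery; Table 6 discontinues. The cross-reference to Section 5.2.3.1 does not say which prevails.

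**4. Overlap inside Table 6.** Hold row: LVEF < institutional limit and B − LVEF ≥ 10. Continue row: LVEF > 45%. Both are met for whole-number LVEF from 46 to limit − 1, with B at least 46 + 10 = 56. The documents give no limit, so it is assumed:

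- limit 45%: no overlap
- limit 50%: 46–49%
- limit 55%: 46–54%

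For example, with baseline 60%, LVEF 48% and limit 50%, the fall is 12 points. One row says hold, the other continue.

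**5. The row for LVEF below 40%.** This row can also overlap the hold row. Take baseline 60%, LVEF 38%, repeat 45%. The low value is not confirmed, so this row does not stop ZW25; the repeat is 15 points under baseline, so the hold row does. Neither row tells the site to restart. The two stop tests add to each other, and the outcome is discontinuation.

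**6. PFS6.** Part 1 subjects treated at the recommended dose enter the Part 2 efficacy analyses (Section 9.3.5). A removed subject stays in the denominator without reaching 24 weeks. With N = 56 assumed (50 plus one cohort of 6), the largest shift is 1/56 = 1.8 points per subject; with N = 50 it is 1/50 = 2.0.

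**The case against.** The best reply is that the removal sentence is loose drafting. Several sections consistently separate treatment from study and keep follow-up going, so a careful site would read it as withdrawal from treatment. The document history makes a leftover plausible: the sentence appears in the Amendment 1 entry, and the ongoing efficacy and survival follow-up came with Amendment 3. That explains the conflict but does not remove it, since the sentence stands in the current text without the approval exception.

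On heart failure, the withholding sentence speaks of ejection fraction and so fits the LVEF DLT more naturally; the text then points to Table 6, and the step-down in Section 5.2.3 is permissive and needs approval. This lowers the risk of a wrong restart, but no sentence sets the order of precedence. In Table 6, the words 'as applicable' soften the continue row without telling a site that the hold row wins.

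Two stronger readings should be set aside. A reader might infer that Section 3.1.2 and Table 6 disagree on withholding for every cardiac DLT; for the LVEF fall both withhold. A reader might also infer that the rows for LVEF below 40% and for the hold contradict each other; they are cumulative, as step 5 shows.

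**Conclusion.** Wrong as written: an internal inconsistency, minor in size. Three parts hold:

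- Section 3.1.2 conflicts with Sections 4.4.1, 4.4.2, 3.1, 6.6 and 7.7.2 on what follows more than 4 weeks off ZW25.
- Section 3.1.2 differs from Table 6 on symptomatic heart failure and on the LVEF recovery threshold.
- The Table 6 hold row and the row for LVEF above 45% overlap with opposite actions in both parts of the study, but only where the institutional limit exceeds 45%.

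The recovery ranges assume that the undefined earlier level means baseline; within the Part 1 window, an LVEF-fall DLT would also need an unscheduled measurement. The documents give no frequency for removals, and the trigger is narrow, so literal loss of AESI, scan and survival follow-up would touch a few Part 1 subjects.

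A reader might infer that the primary endpoint is compromised. The documents do not support that: the shift is at most 1.8 to 2.0 points per removed subject, and PFS6 is reported descriptively with a confidence interval and no decision threshold.

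**What to change.** - In Section 3.1.2, replace removal from the study with: *withdrawn from study treatment per Section 4.4.1, with follow-up per Sections 6.6 and 6.7*.
- In Section 3.1.2, state that Table 6 governs cardiac events, including discontinuation of ZW25 for symptomatic heart failure and the LVEF recovery threshold, and that the step-down permission in Section 5.2.3 does not apply to symptomatic heart failure.
- In Table 6, limit the row for LVEF above 45% to cases that do not meet the hold row.

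The cost is wording edits in an amendment. No visits, procedures or subjects are added, and no sample-size figure changes.
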